8.4.6 Cetuximab: Dose modification and treatment for hypomagnesemia

Hypomagnesemia has been reported in up to 65% of patients following cetuximab therapy. Fatigue, malaise, tremor, ataxia, carpopedal spasm, hyperreflexia, confusion, hallucinations, convulsions and arrhythmias may occur.

Patients should have magnesium concentration monitored at baseline, prior to each cycle of chemotherapy and for up to 8 weeks after the last dose of chemotherapy, or until magnesium has normalised, whichever is the longer. Hypomagnesemia should be corrected by intravenous supplementation if grade 3 (<0.4 mmol/l) or symptomatic. If lesser degrees of hypomagnesemia are detected, oral supplementation may be considered

8.4.7 Irinotecan: General principles of dose modification

Irinotecan dose reductions are permanent

Toxicity grade	Diarrhoea	Radiothera py	Cetuximab	Capecitabine	Irinotecan
1	increase of <4 stools per day over pretreatment level	Continue	100%	100%	Continue
2	increase of 4-6 stools per day over pretreatment levels or moderate cramping	Continue	100%	100%*	Interrupt until grade 0-1; then 100%
3**	increase of 7-9 stools/day or incontinence (if patient continent prior to treatment), severe cramping	Interrupt until grade 0-1	100%	Interrupt until grade 0-1; then 75%	Interrupt until grade 0-1; then 75%
4	increase of => 10 stools per day, grossly bloody diarrhoea, need for parenteral support haemorrhagic dehydration	Interrupt until grade 0-1	Discontinue	Discontinue	Discontinue

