A clinical evaluation will be carried out (doctor/nurse) at the commencement of cetuximab, every week during radiotherapy and for four weeks following completion of treatment to record blood count, biochemical profile, estimated GFR, and toxicity scores (using NCI CTC V.3.0). Serum magnesium is to be monitored weekly for 8 weeks post completion of cetuximab treatment. In patients on anticoagulants or those with an abnormal initial clotting profile, clotting profile is measured weekly during chemotherapy then weekly for four weeks post-termination (and longer if deemed clinically appropriate) if this is abnormal.

An MRI scan will be carried out at six weeks following radiotherapy completion then an attempt at surgery will take place eight weeks post radiotherapy completion.

Following surgery, adjuvant chemotherapy is given according to the discretion of the treating physician but recorded on the relevant CRF.

A sample of formalin-fixed paraffin-embedded tumour tissue removed during surgery will be sent to a central lab for analysis of KRAS mutation status. The tumour tissue will be stored and used in future research studies if the patient has consented to this. Otherwise, it will be returned to the site.

From the point of view of late toxicity, patients will be assessed at 6, 12, 24 and 36 months post completion of radiotherapy.

On confirmed tumour progression further formal follow-up within the trial ceases apart from ultimately recording date and cause of death. Further clinical management, including second-line chemotherapy is at the discretion of the treating physician. On study withdrawal for any reason then the CRF Off Study Form is completed, providing reason for treatment withdrawl and/or complete withdrawl. On patient death, CRF Death Form is (also) completed.

No other concomitant cytotoxic treatment or radiotherapy is permitted during the trial.

Specified dose limiting toxicities:

All toxicities below must adhere strictly to definitions specified in the National Cancer Institute Common Terminology Criteria for Adverse Events v3.0:

 Grade 3 diarrhoea that does not improve to grade 2 or less, within 24 hours on intensive anti-diarrhoeal therapy

- o Grade 4 diarrhoea
- Grade 3 or 4 fatigue
- Grade 3 or 4 neutropenia accompanied by fever (>38°C) or ≥grade 3 infection
- Grade 4 thrombocytopenia (platelet count < 25×10^{9} /L)
- o Grade 4 nausea/vomiting despite full antiemetic treatment

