8.4.8 Dose modification and treatment for acute gastrointestinal toxicity

*If no response to loperamide, reduce capecitabine dose to 75%

** if grade 3, lasts more than 24 hours and delays radiotherapy, stop chemotherapy until recovery

Figure 7: Dose modification for acute GI toxicity.

For grade 1 and 2 diarrhoea, loperamide (2 mg as required up to 8 times per day) can give symptomatic relief.

Radiation treatment will be interrupted when grade 3 or 4 toxicity occurs. Treatment can then be re-commenced after recovery from toxicity. However it is important that recovery to either grade 0 or 1 occurs prior to restarting therapy.

In the event of severe toxicity (grade 3 or 4 diarrhoea), the patient should receive full supportive care. It is recommended that such patients should be admitted to hospital and treated with intravenous fluids, loperamide and antibiotics, especially when there is concomitant grade 3 or 4 neutropenia. In the presence of rapidly falling serum albumin, total parenteral nutrition should be added. If \geq grade 3 gastrointestinal toxicity occurs in the presence of \geq grade 3 neutropenia then GCSF at 30 MU subcutaneously (or equivalent according to local practice) should be added for five days or until recovery to \leq grade 2 neutropenia.

Some patients receiving CRT will experience diarrhoea which may initially present as grade 3 but become controlled by loperamide within a few hours and can then be managed in routine clinical practice as the recommendations above for grade 2 diarrhoea.

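### A patient with grade 3 diarrhoea by stool count, managed as section 8.4.8 recommends, can also meet Figure 7's printed grade 4 definition, and the two rows carry different drug actions

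*Protocol*

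**What the plan says.** Figure 7 gives dose actions for acute gastrointestinal toxicity and prints a definition of each diarrhoea grade in the same rows.

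- **Grade 3** is defined as "increase of 7-9 stools/day or incontinence (if patient continent prior to treatment), severe cramping". Radiotherapy is interrupted and cetuximab stays at 100%. For capecitabine and irinotecan the entry is "Interrupt until grade 0-1; then 75" per cent.
- **Grade 4** is defined as "increase of => 10 stools per day, grossly bloody diarrhoea, need for parenteral support haemorrhagic dehydration". Radiotherapy is interrupted, and cetuximab, capecitabine and irinotecan are each marked for discontinuation.

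The supportive-care text in section 8.4.8 does not separate the two grades: "In the event of severe toxicity (grade 3 or 4 diarrhoea), the patient should receive full supportive care". It continues: "It is recommended that such patients should be admitted to hospital and treated with intravenous fluids, loperamide and antibiotics". It then adds: "In the presence of rapidly falling serum albumin, total parenteral nutrition should be added".

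Section 8.4 ties dose modification to the worst grade under NCI CTC v3.0. The protocol does not define parenteral support, and Figure 7 does not say whether its printed definitions or the CTCAE v3.0 definitions decide the row.

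**The concern.** The rows of a dose-modification table should not overlap, so that a patient's condition points to one action. Here the supportive care recommended for grade 3 diarrhoea includes treatment given parenterally, and a need for parenteral support is printed as a grade 4 feature. Following the text can therefore move a patient from the grade 3 row to the grade 4 row with no change in stool count. The worst-grade rule then points to the grade 4 action.

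At stake is whether a patient resumes capecitabine and irinotecan at a reduced dose with cetuximab unchanged, or stops all three drugs permanently. Section 13 names diarrhoea as the most common serious toxicity of irinotecan-containing chemoradiation. Two sites that both follow the protocol could treat the same patient differently, so drug exposure would partly reflect local reading and admission practice. If sites carry Figure 7's grade into their reports, any separate count of grade 3 and grade 4 diarrhoea would be affected too.

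**Working it through.** The protocol states no figure to reproduce on this point. The check is a side-by-side reading, followed by simple arithmetic for size.

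**Does the overlap exist?**

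1. Take a patient with 8 extra stools per day. By the count in Figure 7 this is grade 3, in the range 7 to 9.
2. Section 8.4.8 recommends admission and intravenous fluids for grade 3 or 4. If albumin falls rapidly, parenteral nutrition is added.
3. *With parenteral nutrition:* on any ordinary reading the patient needs parenteral support, which is a printed grade 4 feature. Both rows fit.
4. *With intravenous fluids only:* both rows fit if parenteral support includes fluids. Only the grade 3 row fits if it means nutrition alone. The protocol does not say which.
5. Under the worst-grade rule in section 8.4, wherever both rows fit on the printed definitions, the grade 4 action applies.

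**How many patients could be concerned?**

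Inputs from section 13: 80 patients; grade 3 or 4 diarrhoea in 20% of the predecessor trial; more than 30% regarded as unacceptable.

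- 0.20 × 80 = 16
- 0.30 × 80 = 24

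These are expected numbers with any grade 3 or 4 diarrhoea. Only those who are grade 3 by stool count and need parenteral care are in dispute, so 16 to 24 is a ceiling at those rates. The protocol gives no rate of admission, intravenous fluids or parenteral nutrition from which to narrow it. In the predecessor trial 20% of 91, about 18 patients, had such diarrhoea, and all but one were grade 3. The grade 3 group is therefore likely to be the larger one.

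**What differs between the two rows for one patient?**

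Inputs from section 8.2.1: irinotecan 60 mg/m² × 4 = 240 mg/m² planned. Assume onset after the second dose, and that doses skipped during an interruption are not made up. A 75% dose is 0.75 × 60 = 45 mg/m².

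| Path | Irinotecan received (mg/m²) | Share of plan |
|---|---|---|
| Grade 4 row, discontinued | 120 | 120/240 = 50% |
| Grade 3 row, no dose skipped | 120 + 2 × 45 = 210 | 87.5% |
| Grade 3 row, one dose skipped | 120 + 45 = 165 | 68.75% |
| Grade 3 row, both skipped | 120 | 50% |

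The difference is therefore 0 to 37.5 percentage points of planned irinotecan.

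For cetuximab the plan is 400 + 5 × 250 = 1650 mg/m². Stopping after the second radiotherapy week gives 400 + 2 × 250 = 900 mg/m², or 900/1650 = 54.5%. The grade 3 row as printed keeps cetuximab at 100%.

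**The case against.** The strongest reply is that the protocol already names a grading scale. Section 8.4 refers to NCI CTC v3.0 for dose modification, section 15.2.1.3 uses CTCAE v3.0 for severity, and section 9.1 uses it for toxicity assessment. On that view Figure 7's wording is only a reminder. Section 8.4.8 also treats a patient receiving the supportive package as possibly still grade 3. A footnote to Figure 7 keeps prolonged grade 3 diarrhoea on a path that stops chemotherapy only until recovery. Need for parenteral support could then be read as a description of severity and not as receipt of the recommended fluids. The admission advice is a recommendation, and grade 3 diarrhoea quickly controlled by loperamide may be managed as grade 2. The separators in the grade 4 cell may also have been lost in text extraction.

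Much of this stands, and it limits the reach of the point. It does not remove the overlap. Figure 7 prints definitions in the table that sites will use to choose a dose, and nothing ranks them against CTCAE v3.0. Whether they depart from that scale cannot be checked here, because it is not reproduced in the protocol. The severity-descriptor reading still leaves a patient who needs parenteral nutrition in both rows. Whatever the lost separators, the parenteral-support wording sits in the grade 4 row.

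A reader might infer wider damage, which the protocol does not support:

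- **Toxicity endpoint and stopping count.** The secondary endpoint (sections 1.1 and 8.1) and the diarrhoea stopping count of 17 (section 13) both pool grades 3 and 4. Moving a patient between them changes neither.
- **Dose-limiting toxicities.** Section 8.1 lists "Grade 4 diarrhoea" without condition, and grade 3 only if it does not improve within 24 hours. The same list is tied strictly to CTCAE v3.0 definitions, so Figure 7's wording does not create a dose-limiting toxicity.
- **Most grade 3 patients losing all three drugs.** No admission or parenteral-care rate is given that would support this.
- **A loss of 37.5 points of irinotecan.** This is the top of a range that reaches zero.

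**Conclusion.** The point holds in a limited form. As written, a patient who is grade 3 by stool count and managed as section 8.4.8 recommends can also meet Figure 7's grade 4 row. The conflict is definite where parenteral nutrition is given. Where only intravenous fluids are given, it turns on an undefined term.

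The effect falls on dose action, on drug exposure and on any separate reporting of grades 3 and 4. The number of patients is unknown, with an expected ceiling of 16 to 24 of 80 if the true rate of grade 3 or 4 diarrhoea is 20% to 30%. The irinotecan difference of 0 to 37.5 points assumes onset after two doses and no make-up of skipped doses. The cetuximab contrast takes the grade 3 row at its printed 100%.

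The matter merits correction because it bears on permanent discontinuation for the leading expected toxicity. It says nothing against the primary endpoint, the pooled toxicity endpoint or the safety monitoring rule.

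**What to change.** Reconcile three things: the grade definitions printed in Figure 7, the supportive-care text in section 8.4.8, and the CTCAE v3.0 grading that section 8.4 invokes. State which definition governs dose action, and say what parenteral support means if the term is kept. The test of the revised text is that care recommended for one grade does not by itself place the patient in the next. Which grade definition and which drug action apply is a clinical decision for the sponsor, and no view is offered here.

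The cost is an amendment to one table and one paragraph, with a memo to sites. No extra procedures, visits or patients are needed, and the sample size and stopping count stay as they are.

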8.4.8 Dose modification and treatment for acute gastrointestinal toxicity

*If no response to loperamide, reduce capecitabine dose to 75%

** if grade 3, lasts more than 24 hours and delays radiotherapy, stop chemotherapy until recovery

Figure 7: Dose modification for acute GI toxicity.

For grade 1 and 2 diarrhoea, loperamide (2 mg as required up to 8 times per day) can give symptomatic relief.

Radiation treatment will be interrupted when grade 3 or 4 toxicity occurs. Treatment can then be re-commenced after recovery from toxicity. However it is important that recovery to either grade 0 or 1 occurs prior to restarting therapy.

In the event of severe toxicity (grade 3 or 4 diarrhoea), the patient should receive full supportive care. It is recommended that such patients should be admitted to hospital and treated with intravenous fluids, loperamide and antibiotics, especially when there is concomitant grade 3 or 4 neutropenia. In the presence of rapidly falling serum albumin, total parenteral nutrition should be added. If \geq grade 3 gastrointestinal toxicity occurs in the presence of \geq grade 3 neutropenia then GCSF at 30 MU subcutaneously (or equivalent according to local practice) should be added for five days or until recovery to \leq grade 2 neutropenia.

Some patients receiving CRT will experience diarrhoea which may initially present as grade 3 but become controlled by loperamide within a few hours and can then be managed in routine clinical practice as the recommendations above for grade 2 diarrhoea.

8.4.9. Dose modification in the event of renal toxicity

Although neither cetuximab nor capecitabine is nephrotoxic, serum creatinine and calculated GFR should be monitored weekly during radiotherapy. If the calculated GFR deteriorates to 50 ml/min or below a formal measurement (24 hour urine or EDTA) is required. Dose reduce capecitabine as shown below. If GFR falls below 30 ml/min the patient should stop capecitabine.

Formal GFR	Radiotherapy	Capecitabine	Cetuximab	Irinotecan
> 50 ml	Continue	100%	100%	100%
30-50 ml	Continue	75%	100%	100%
< 30 ml	Continue	Do not give	100%	100%

Figure 8: Dose modification for renal toxicity

8.4.10 Dose modifications in the event of other non-haematological toxicities

The following table represents a general guideline for dose reduction recommendations for relevant side effects that are associated with radiotherapy or particular chemotherapy agents and which are not described in the previous sections.

Toxicity grade CTC criteria	Radiotherapy	Capecitabine	Cetuximab	Irinotecan
1	Continue	100%	100%	100%
2	Daily review	Interrupt until grade 0 or 1; then 100%	Interrupt until grade 0 or 1; then 100%	Interrupt until grade 0 or 1; then 100%
3	Daily review	Interrupt until grade 0 or 1; then 75%	Interrupt until grade 0 or 1; then 75%	Interrupt until grade 0 or 1; then 75%
4	Discontinue treatment unless symptoms settle to grade 0-1 within two weeks	Discontinue treatment	Discontinue treatment	Discontinue treatment

Figure 9: Dose modifications for other non-haematological toxicities

WBC (10 ⁹ /l)	Neutrophils (10 ⁹ /I)	Platelets (10 ⁹ /l)	Radiotherapy	Capecitabine	Cetuximab	Irinotecan
≥ 3 (grade 1)	≥ 1.5 (grade 1)	≥ 75 (grade 1)	Continue	100%	100%	100%
≥2 - <3 (grade 2)	≥ 1.0 <1.5 (grade 2)	≥ 75 (grade 1)	Continue	100%	100%	100%
≥1 - <2 (grade 3)	≥ 0.5 - <1.0 (grade 3)	≥ 50 - <75 (grade 2)	Interrupt until grade 0-1	Interrupt until Grade 0-1; then 75%	100%	Interrupt until Grade 0-1; then75%
<1 (grade 4)	<0.5 (grade 4)	<50 (grade 3 or 4)	Interrupt until grade 0-1	Interrupt; if recovers to Grade 0-1 discuss with TMG prior to 50%	100%	Interrupt; if recovers to Grade 0-1 discuss with TMG prior to 50%

8.4.11 Modifications of drug therapy for haematological toxicity

Figure 10: Dose modifications for haematological toxicities

8.4.12 Unplanned breaks in radiotherapy

During unplanned breaks in radiotherapy not due to treatment-related toxicity (for example machine breakdown or bank holidays) chemotherapy will be interrupted and then resume to run concurrently with radiotherapy once radiotherapy resumes.

9 Assessments

9.1 Assessment investigations

9.1.1 Baseline: Prior to registration

- MRI scan (within 35 days of registration)
- FBC, U&Es, LFTs, serum magnesium (within 7 days)
- Calculated GFR (within 7 days) using Cockcroft formula (Appendix 4) (if ≤ 50ml/min, formal measurement using 24 hour urine/EDTA)
- CEA (within 4 weeks)
- Clotting profile (within 4 weeks)
- Vital signs: blood pressure, pulse rate, temperature (within 7 days)
- Height & weight (within 7 days)
- WHO performance status (within 7 days)
- Baseline toxicity assessment (using NCI CTCAE V.3.0)

9.1.2 During treatment phase: within 48 hours prior to cetuximab/irinotecan

infusions

Weekly

- FBC, U&Es, LFTs
- Calculated GFR using Cockcroft formula (Appendix 4) (if ≤ 50ml/min, formal measurement using 24 hour urine/EDTA)
- Clotting profile if abnormal at baseline
- Serum Magnesium
- Toxicity assessment (using NCI CTCAE v3.0)
- Capecitabine compliance
- Blood samples for ancillary studies (at start of CRT only) if patient has consented to these (see Section 19)

During each cetuximab infusion

• Vital signs (blood pressure, temperature, pulse, respirations) to be monitored before during and immediately on completion of infusion, and 1 hour post-infusion.

9.1.3 Post chemoradiation

Weekly for 4 weeks

- FBC, U&Es, LFTs
- Serum Magnesium (continue for 8 weeks in total or until magnesium has normalised; whichever is the longer)
- Toxicity assessment (using NCI CTCAE v3.0)

6 weeks post chemoradiation

- CEA
- Pelvic MRI scan

8.1.4 Post-surgery

• Send tumour tissue blocks for KRAS testing (see Section 19)

9.1.5 Follow-up phase (all assessments are from the end of chemoradiotherapy)

- 6 months: Physical exam & late toxicity assessment
- 12 months: Physical exam & late toxicity assessment
- 24 months: Physical exam & late toxicity assessment
- 36 months: Physical exam & late toxicity assessment

All other investigations if clinically indicated at the discretion of the clinician.

9.2 Efficacy endpoints

Resectability will be defined in terms of:

- R0 resection rate i.e. the carcinoma is resected with margins clear by >1mm.
- R1 resection rate i.e. the carcinoma has microscopically-involved margins
- R2 resection rate i.e. the carcinoma is resected but has macroscopically-involved margins at the time of surgery.

Response rate will be defined in terms of:

• Pathological complete response (pCR) i.e. no residual viable carcinoma on extensive examination of the resected specimen.

The following will also be recorded:

- 'Near' pCR i.e. microscopic foci of occasional single carcinoma cells remaining on extensive examination of the specimen.
- Decrease in size of the carcinoma in superior-inferior and transaxial dimensions on comparing pre- and post- CRT MRI scans.
- Change in MRI-defined TNM stage of tumour on pre- and post-CRT MRI scans.
- TNM stage of resected specimen compared to predicted on pre-CRT MRI scan.

The denominator will be total numbers of subjects recruited for the trial and commencing CRT treatment.

The following categories of patient will be distinguished:

- Patients undergoing CRT and an attempt at laparotomy but tumour not resected because found to be too locally advanced at surgery.
- Patients undergoing CRT and an attempt at laparotomy but tumour not resected because found to have developed metastatic disease.
- Patients undergoing CRT and an attempt at laparotomy but tumour not resected because of other reasons.
- Patients undergoing CRT but not undergoing surgery because tumour remains too locally-advanced on restaging MRI.

Disease free survival - the 'event' will be time from randomisation to confirmation of local failure or recurrence, distant metastases, or death from any cause, whichever occurs first, disease-free patients being censored at the date last seen.

Local failure – A local failure is defined as:

- pelvic disease extent is considered unresectable (after pre-op CRT has been given and reassessment has taken place).
- when at laparotomy there is residual macroscopic pelvic malignancy.
- when during the follow up period (after macroscopic clearance of tumour was achieved) there is evidence of confirmed local recurrence. Confirmed local recurrence includes biopsy confirmation of local recurrence, unequivocal local recurrence on imaging (MRI scanning and /or PET) or equivocal local recurrence on imaging in the definite absence of metastatic disease and in the presence of a rising CEA.

Therefore local failure will be the time from randomisation to the first confirmation of local failure as defined above.

Local failure-free survival will be the time from randomisation to local failure or death whichever occurs first, survivors with no local recurrence being censored at the date last seen.

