2.5 Chemoradiation with capecitabine and irinotecan

A number of groups have evaluated this combination (reviewed in Glynne-Jones et al ,06). Klautke updated experience with irinotecan (CamptoTM) and capecitabine at ASCO 2006 [Klautke, 06]. Acceptable toxicity was reported for a capecitabine regimen of 750mg/m² bd for weeks 1-3 and 4-5 combined with irinotecan 50mg/m² weekly (n=20) and 60mg/m² (n=11) weekly x6 combined with 50.4Gy +/- boost of 5.4Gy. Mitchell et al (2006) have also reported early results using a regimen of capecitabine 625mg/m² bd continuous with irinotecan 50mg/m² weekly x 4 and 50.4Gy with 3(27%) patients achieving pCR.

Kennedy et al (2002) delivered radiotherapy using 54 Gy as preoperative downstaging treatment in rectal cancers. Patients received weekly infusions of irinotecan at 50 mg/m²/week. In addition, they received capecitabine at 500 mg bd, 650 mg bd or 1,000 mg bd on radiotherapy days. The Maximum Tolerated Dose (MTD) had not been reached at a dose of 1,000 mg bd of capecitabine. All patients were staged uT3 or uT4 prior to chemoradiation. All were downstaged by at least one T-stage and there was one pCR.

In the UK, the NWCOG completed recruitment to a larger phase I/II study in December 2006. There were 100 patients in the phase II element of the study. Initial phase II data were presented at ASCO 2006 [Gollins et al,'06]. 56 patients were treated at the recommended dose level (Irinotecan 60 mg/m² weekly weeks 1,2,3,4 plus capecitabine 650 mg/m² bd po 7 days per week during the 5 weeks of radiotherapy). Fourteen (25%) of these developed a grade 3 or 4 toxicity. Most were grade 3. Nine (20%) of these were diarrhoea (8 grade 3, one grade 4); two were lethargy (both grade 3); one was febrile neutropenia (grade 3). At the recommended dose the mean amount of the intended dose received of radiotherapy, irinotecan and capecitabine are 97%, 92% and 86% respectively. An analysis of efficacy is based on the 81 patients in both the phase I and phase II components. Seven (9%) did not undergo resection, two developed liver metastases, four deteriorated in terms of general condition and one died of pneumonia. Seventy four (91%) underwent resection, of which 65 were CRM negative [80% intention to treat], 19 (29%) had a complete pathological response (pCR) and11 (17%) had microfoci of disease only (scattered individual cells).

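### The local failure definition gives no clear route to an event for a patient whose primary is never operated on for reasons other than pelvic extent

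*Protocol*

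**What the plan says.** Section 9.2 (Efficacy endpoints) defines local failure by three routes:

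- (a) "pelvic disease extent is considered unresectable (after pre-op CRT has been given and reassessment has taken place";
- (b) "when at laparotomy there is residual macroscopic pelvic malignancy";
- (c) "when during the follow up period (after macroscopic clearance of tumour was achieved) there is evidence of confirmed local recurrence".

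LFFS runs to local failure or death, "survivors with no local recurrence being censored at the date last seen". DFS runs to "confirmation of local failure or recurrence, distant metastases, or death from any cause, whichever occurs first", with "disease-free patients being censored at the date last seen". The term disease-free is not defined.

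The same section sets the denominator as everyone recruited who starts CRT. It lists four categories of unresected patient to be distinguished. Three involve an attempted laparotomy. The only one without surgery is "Patients undergoing CRT but not undergoing surgery because tumour remains too locally-advanced on restaging MRI".

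Section 2.5 reports on the predecessor irinotecan/capecitabine series of 81 patients: "Seven (9%) did not undergo resection, two developed liver metastases, four deteriorated in terms of general condition and one died of pneumonia".

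**The concern.** Each route depends on a condition that some unoperated patients will not meet. Consider a patient who completes CRT and is then not operated on because of declining condition, refusal or metastases on the restaging scan. Pelvic extent was not the reason, there was no laparotomy, and clearance was never achieved. If the primary is later shown to persist or grow, the definition does not plainly make that a local failure.

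LFFS would then carry the patient as event-free until death. DFS takes its local component from the same definition, so it would record nothing until metastasis or death. Both are named secondary endpoints, and the error runs one way: event-free proportions are too high while such patients are alive. The protocol fixes this definition itself, so the gap is in a stated rule and is not a detail left for an analysis plan.

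**Working it through.** **Step 1. Map the reasons for no surgery onto the definitions in section 9.2.**

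| Patient without laparotomy | Route (a) | Route (b) | Route (c) | LFFS | DFS |
|---|---|---|---|---|---|
| Too locally advanced on restaging | yes | no | no | event | event |
| General deterioration or refusal | not on extent | no | no | censored while alive | no event before metastasis or death |
| Metastases on restaging | not on extent | no | no | censored while alive | event (metastases) |
| Died before surgery | not needed | no | no | event (death) | event (death) |

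Patients who are opened and left with visible pelvic tumour enter by route (b), whatever the reason for non-resection. The gap concerns patients with no laparotomy.

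**Step 2. Check whether follow-up closes the gap.** Section 9.1.5 schedules physical examination and late toxicity at 6, 12, 24 and 36 months, with other investigations at the clinician's discretion. No later reassessment of resectability is scheduled. Route (a) therefore has no stated trigger or date after the post-CRT reassessment. Sections 8.1 and 10.1 end formal follow-up at confirmed progression, apart from date and cause of death. Pelvic events after metastasis may therefore go unrecorded.

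**Step 3. Reproduce the protocol's own figures (section 2.5).** Unresected: 7/81 = 8.6%, stated as 9%. Resected: 74/81 = 91.4%, stated as 91%. Both agree. The seven are 4 with deterioration, 2 with liver metastases and 1 death (4 + 2 + 1 = 7). None is attributed to local extent.

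**Step 4. Size the group, using the planned 80 patients (section 13).** The intervals are exact 95% (Clopper-Pearson).

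- No clear local failure route: 4 + 2 = 6, and 6/81 = 7.4% (2.8% to 15.4%). In 80 patients: 80 × 6/81 = 5.9, range about 2 to 12.
- Neither a local failure nor a DFS event before metastasis or death: 4/81 = 4.9% (1.4% to 12.2%). In 80 patients: 80 × 4/81 = 4.0, range about 1 to 10.
- Chance of at least one of the latter in 80, at a rate of 4/81: 1 − (77/81)^80 = 98%.

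**Step 5. Convert to bias.** If all such patients were alive with pelvic disease at a given time, the event-free proportion would be too high by up to about 7 percentage points for LFFS and about 5 for DFS. Death counts in both endpoints, so the excess shrinks as these patients die.

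**The case against.** The strongest reply is that the gap is narrower than it looks. Much of that stands.

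- **Later growth.** A reader might infer that growth of an unresected primary can never be a local failure. The text does not go that far. Route (a) has no upper time limit and needs neither laparotomy nor earlier clearance, so growth later judged unresectable could enter by it. What is missing is a trigger and a date, which leaves the outcome to each investigator.
- **DFS.** A reader might infer that the protocol declares patients with tumour in place disease-free. It does not, because the term is undefined. Their event-free status follows from the list of events. For LFFS the censoring text applies directly.
- **Tumour status.** Section 2.5 reports 19 complete pathological responses in the predecessor series, so some unoperated patients may have no viable tumour. It gives no pelvic status for the four who deteriorated.
- **Patient categories.** Section 9.2 does not call its four categories exhaustive. Section 5 requires WHO performance status 0 or 1 and excludes patients unsuitable for surgery because of co-morbidity. This should reduce the group but cannot remove it, since deterioration and refusal arise after entry.
- **R0 against LFFS.** Failing R0 while remaining free of local failure is not a contradiction. An R1 patient can do the same.
- **Decision impact.** Section 13 rests the decision on R0, and unresected patients stay in that denominator. No benchmark is stated for DFS or LFFS, so a reading that the gap tilts the trial's decision is unsupported.

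None of this supplies a clear route for documented pelvic persistence or growth in a patient who was never operated on.

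**Conclusion.** The point holds as a gap in the definition of two secondary endpoints. The direction is upward for both LFFS and DFS.

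The size is a ceiling at the predecessor's observed rates: about 6 of 80 for LFFS and about 4 of 80 for DFS, with the sampling ranges given above. It rests on these assumptions:

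- the predecessor's reasons for non-resection carry over to this trial;
- none of the six had a laparotomy showing pelvic residue, or was judged unresectable on extent, then or later;
- they have pelvic disease and remain alive.

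The protocol gives no expected rate for this trial and no survival for those six, so how long the bias would last cannot be stated. The primary endpoint and the go/no-go rule do not change.

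**What to change.** 1. Extend the local failure definition in section 9.2. Confirmed persistent or progressive pelvic disease, in a patient whose primary was never resected with macroscopic clearance, should be a local failure dated at that confirmation. It then counts in both LFFS and DFS. The confirmation criteria already given for local recurrence can be reused. The text should say whether the six-week MRI can serve as the confirmation.
2. Add a sensitivity analysis that counts non-resection for any reason as an event, dated at the decision not to operate or at the planned surgery date. This is better as a sensitivity analysis than as the main rule, because it would also label refusal, or a complete response without surgery, as local failure. It also covers patients whose pelvic status goes unrecorded once formal follow-up stops at metastasis.
3. Add the no-surgery reasons to the listed categories: unfit, refused, metastases on restaging, died.

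The cost is a few lines of text. Surgery, withdrawal and death forms already exist. Confirming pelvic status still depends on investigations that the protocol leaves to discretion, so some events may be dated late. Reported LFFS and DFS become slightly less favourable.
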